4. SELECTION AND ENROLLMENT OF PARTICIPANTS

4.1: Inclusion Criteria

Participants must meet all of the inclusion criteria to participate in this study. Criteria include:

- 1) Between 18-35 years of age
- 2) All genders
- 3) Willing to complete two study visits over 2-3 weeks
- 4) Able to read and communicate in English

4.2: Exclusion Criteria

All candidates meeting any of the exclusion criteria at baseline will be excluded from study participation.

Exclusion criteria include:

- 1) Current lower back condition with pain, numbness or tingling that radiates down the legs
- 2) Active treatment for a major medical illness, such as heart disease, uncontrolled diabetes or hypertension, malignancy, autoimmune, or immune deficiency disorder

- 3) History of vasculitis, intracranial mass, clotting disorder (including medication-induced, e.g., warfarin)
- 4) Current skin malignancy on scalp
- 5) Cognitive dysfunction preventing informed consent
- 6) Pending or currently receiving benefits from personal injury litigation, including worker's compensation
- 7) Chronic long-term disability related to lumbosacral injury/symptoms
- 8) Epilepsy

4.3: Study Enrollment Procedures

Sample Size and Population

Target Population. The target population will be healthy young adults between the ages of 18-35. Healthy young adults are chosen as the target population because this is a) a pilot study and b) the expectation of rapid subject recruitment and excellent retention.

Recruitment Estimates. Approximately 60 healthy young adults will be screened to achieve a pre-intervention sample size of 44 subjects. We expect at least 38 of the 44 to complete the 2-week intervention, which will provide adequate power to test Aim 1.

Sources of Subjects

The primary source for recruitment will occur through the Exercise and Sports Science Department. Additional recruitment for potential subjects will occur at other sites around UNC. The study will be listed on the NC TraCS research recruitment website www.jointheconquest.com.

Consenting

All subjects will be assessed for eligibility on the basis of their medical condition by the PI, [name], a board certified chiropractor specializing in conservative care of musculoskeletal conditions. Interested individuals will sign a permission to contact form. Prior to the initial visit with a study team member, the subject will complete a telephone screen with telephone consenting. If the potential participant remains eligible, a study team member will schedule an appointment for the first study visit.

Consenting Process

Informed consent forms (ICFs) will be reviewed with the patient by either the study coordinator, the project supervisor, or the co-investigator. The study team member will read the ICFs to the patient as they follow along. Any questions the patient may have will be answered accordingly. After reviewing the consent, a patient may decline to participate, sign to participate at the time of the meeting, or take the ICFs home with them to be signed at a later time. The patient will be considered to be a subject at the time of signing the consent. Persons who cannot sign for themselves will not be recruited.

Documentation

Documentation of each study visit will include a visit checklist signed by the study team personnel completing the visit.

Randomization

The study coordinator randomizes eligible subjects into one of the two arms at the time of their first visit using a computer-generated blocked randomization process. Please see Section 9.2 for details.

5. STUDY INTERVENTION

5.1: Intervention, Administration, and Duration

CLRT is a complementary or alternative intervention that incorporates principles of laser acupuncture with chiropractic cranial reflexology. Instead of acupuncture points derived from TCM, CLRT involves low level laser stimulation of two distinct cranial microsystems discovered by chiropractors. The first map of cranial reflex points/pathways (CRP) was originally discovered by a doctor named Jack Elvidge using Applied Kinesiology, and each CRP corresponds to a major muscle or group. These soft-tissue CRPs are either points or directional lines on the skull, and they appear to have an influence on the particular muscle's tonus and strength. It was originally found that stimulating a linear reflex with digital pressure in one direction relaxed the muscle's tone, and stimulating it in the opposite direction increased the tonicity.

The second set of CRPs used in CLRT were discovered by David Denton, D.C., and consists of points that relate to each vertebra of the spine, rib, sacroiliac joint, sacrum and coccyx. Denton found that subtle manipulations of these points affected the position and function of misaligned vertebra in manner similar to adjusting them directly. [name] developed CLRT after postulating that the CRP's had similar optical properties to the acupuncture meridians, and would respond to coherent light in a similar manner. Upon clinical experimentation, he found that the cranial reflexes were in fact extremely responsive to low doses of laser light. The major goal of CLRT is to quickly decrease in pain, increase joint range of motion, and achieve lasting functional improvements. CLRT can be performed with a range of laser powers from 5milliwatts (mW) to 500mW with similar results, and wavelengths from 405nm-840nm have been used successfully.

The first visit will last approximately 1 hour and the second visit will take 30 minutes.

5.2: Concomitant Interventions

5.2.1: Allowed Interventions

Subjects will be allowed to partake in their usual exercise and physical activities.

5.2.2: Required Interventions

Participation in both study arms of the crossover trial.

5.2.3: Prohibited Interventions

None.

5.3: Adherence Assessment

We will define study adherence as completion of both study visits.

6. STUDY PROCEDURES

6.1: Schedule of Evaluations

Activity	Visit 1 (Week 1)	Visit 2 (Week 2)	Check-in Call (Week 3)
People involved in visit/activity:	Study Coordinator, Investigator and Research Assistant	Investigator and Research Assistant	Research Assistant
Location:	Neurophysiology Lab	NL	Phone
Eligibility Criteria Review	X		
Informed Consent Review	X		
Randomization	X		
Musculoskeletal History	X		
Hamstring Tightness Questionnaires	X	X	
90-90 KEA	X	X	
Handheld Dynamometry	X	X	
Intervention	X	X	
Expectation of Benefit	X		
Perceived value of the intervention		X	
Follow up			X

6.2: Description of Evaluations

6.2.1: Screening Evaluation and Consenting

Screening

A brief telephone call by the research assistant that will cover inclusion/exclusion criteria and components of the study will be completed. If subject is interested, they will be invited to consent and enroll in the study.

Consenting

Interested participants will travel to UNC Neurophysiology Lab at Fetzer Hall to meet with a Study Coordinator or Research Assistant to review consent forms and sign and date (in a private room).

After participants sign the consent, their musculoskeletal history questionnaire will be reviewed by the PI to ensure that the patient has no outlying medical issues that would exclude participation.

6.2.2: Enrollment, Baseline, and/or Randomization

Enrollment

Subjects are enrolled at time of signing the consent form. The analysis will be done under an Intention to Treat.

Baseline Assessments

Age, gender, hamstring injury questionnaire, perceived hamstring tightness scale, activity level.

Randomization

Randomization occurs at the end of the baseline and screening phase immediately prior to starting the intervention.

6.2.3: Blinding

Subjects and assessors will be blinded to treatment allocation. The subject will be face down, eyes closed, and wearing protective eyewear that blocks the specific wavelength of the laser light during the intervention.

Individuals authorized to break the blind include the PI and study statistician.

Circumstances for breaking the blind include the development of a Serious Adverse Event (SAE) or recurrent Adverse Event (AE) apparently related to the research interventions.

The procedure for breaking the blind is to have the research assistant inform the PI or the study statistician of the allocation of the subject.

After each treatment session, the participants will complete a de-blinding questionnaire administered by the assessor providing a dichotomous 'yes' or 'no' answer as to whether active treatment was received. This response will be followed by a second question regarding how certain they were that active treatment was received on a 0–10 numeric rating scale (NRS), where 0 represents absolutely uncertain and 10 represents absolutely certain.

6.2.4: Study Visits

Study visits will ideally be one week apart. (See Section 6.1 for Schedule of Evaluations table.)

- **Visit 1:**

- Inclusion / Exclusion Criteria
- Consenting: Subject Enrollment
- Study questionnaires: Hamstring Injury questionnaire
- Randomization
- KEA

- HHD
- PPT
- Intervention
- Post KEA
- Post HHD
- Post PPT
- De-blinding questionnaire

- **Visit 2: Week 2-3**

- KEA
- HHD
- PPT
- Intervention
- Post KEA
- Post HHD
- Post PPT
- De-blinding questionnaire

6.2.5: Completion

- Study questionnaires:
 - Expectation of benefit/ Believability scale
- Evaluation for participants who discontinue study intervention early

Potential reasons for early termination include: subject no longer interested, adverse events, subject not able or willing to follow the protocol, subject moved away from the area or prolonged travel.

If subjects withdraw early, the PI or his designee will attempt to follow-up by telephone to inquire about health status as it relates to adverse events experienced by the subject leading to early discontinuation of participation.

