- 1) **Expectation of benefit:** Measured with a modified Borkovec and Nau scale(36). This instrument provides an assessment of credibility of each intervention using an adaptation of a validated credibility scale previously developed for psychological studies for purposes of comparing the two treatment arms. This instrument has been successfully adapted for use in other conditions such as chronic pain and migraine headache. It will be administered after each subject completes the second visit.
- 2) **Perceived value of the intervention** is measured at the end of the active intervention via questionnaire. At the end of the post-intervention phase, subjects will be invited to participate in a brief post-study interview to assess their overall impressions of the treatment.

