Appendix C.c : Modified Borkovec and Nau Expectation of Benefit/ Credibility Form (version 1.0)

Expectation of Benefit / Credibility**INSTRUCTIONS**

You have been given details about the treatments you are learning in this study. We are interested in obtaining your impressions about and reactions to the procedures presented to you thus far. Please answer the questions below by first finding the number on the scale that most accurately describes your impressions and then by filling in the oval that corresponds with that number.

1. How logical does this type of intervention seem to you for improving muscle function?

Not logical										Very logical	
0	1	2	3	4	5	6	7	8	9		
											

2. How confident are you that this intervention will be successful in improving muscle function?

Not at all confident										Very confident	
0	1	2	3	4	5	6	7	8	9		
											

3. How confident would you be in recommending this intervention to a friend who has a problem with their hamstrings?

Not at all confident										Very confident	
0	1	2	3	4	5	6	7	8	9		
											

4. How important do you think it is that we make this intervention available to others who experience muscle problems?

Not at all important										Very important	
0	1	2	3	4	5	6	7	8	9		
									

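### The credibility form has conflicting timings, and a single form given after Visit 2 cannot separate CLRT from sham

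*Combined protocol and SAP*

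**What the plan says.** **Purpose.** Section 3 (patient-reported variables) introduces the modified Borkovec and Nau scale: "This instrument provides an assessment of credibility of each intervention", and it is used "for purposes of comparing the two treatment arms". Section 5.2.2 requires of every subject: "Participation in both study arms of the crossover trial".

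**Timing.** The plan gives two answers:
- Section 6.1 schedule: "Expectation of Benefit X", with the mark under Visit 1 and nothing under Visit 2.
- Section 3: "It will be administered after each subject completes the second visit".
- Section 6.2.5 (Completion) agrees with section 3, listing: "Expectation of benefit/ Believability scale".
- Section 6.2.4: the form is in neither the Visit 1 nor the Visit 2 list. That section refers the reader back to the 6.1 table.

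**The form.** The Expectation of Benefit / Credibility form (headed Appendix C.c) has one set of four items. Its instruction reads: "We are interested in obtaining your impressions about and reactions to the procedures presented to you thus far". Item 2 is typical: "How confident are you that this intervention will be successful in improving muscle function". As printed, it has no field for visit, period or treatment.

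**Analysis.** Section 9.6 does not mention the credibility score.

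**The concern.** There are two linked problems. First, staff cannot follow both timings, and the visit lists do not settle which is meant.

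Second, the purpose in section 3 needs one rating for CLRT and one for sham, or at least ratings from groups that have so far had only one of them. Under the timing in sections 3 and 6.2.5, each subject has received both treatments by the time of the form, and the form asks about an unnamed intervention and everything presented so far.

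At stake is a check on whether the sham was as convincing as CLRT. That has some bearing on how the results are read. The knee extension angle (KEA) is taken at the stretch the subject reports as strong but tolerable, and the pain pressure threshold (PPT) at the point where the subject says pressure has become pain, so both can respond to expectation.

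**Working it through.** The plan gives no figure for the credibility comparison, so there is none to reproduce. The check sets out what each timing can deliver and then how precise it would be.

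**Step 1: what each timing delivers**

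| When the form is given | Treatments received so far | CLRT-versus-sham comparison |
|---|---|---|
| Visit 1, before treatment | none | none |
| Visit 1, after treatment | the period-1 treatment only | between randomised groups, period 1 only |
| After Visit 2, one form | both | none; the rating covers both |
| Visit 1 after treatment, plus one form after Visit 2 | one, then both | period 1 only; the second rating still covers both |

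The 6.1 table does not say whether the Visit 1 form comes before or after treatment. Its row lies below the Intervention row, but row order there is not time order: Randomization is listed above Musculoskeletal History, whereas 6.2.4 puts the questionnaires before randomization.

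**Step 2: inputs for precision**
- 44 enrolled and 38 expected completers (sections 4.3 and 9.2).
- Equal allocation to the two sequences (section 3), so 44/2 = 22 per group. If completers split evenly, 38/2 = 19 per group.
- Correlation r between a subject's two credibility ratings: not given, so r = 0, 0.25, 0.50 and 0.75 are assumed.
- Equal SD under both treatments: assumed. Results are in SD units.

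**Step 3: Visit 1 form after treatment (two groups of n)**

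Expected 95% CI half-width = t(0.975, 2n − 2) × √(2/n)
- n = 22: 2.018 × 0.3015 = 0.608 SD
- n = 19: 2.028 × 0.3244 = 0.658 SD

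**Step 4: one form after each session, 38 completers**

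Half-width = t(0.975, 36) × √(2(1 − r)/38), with 36 degrees of freedom after adjusting for period
- r = 0: 2.028 × √(2/38) = 0.465 SD
- r = 0.25: 2.028 × √(1.5/38) = 0.403 SD
- r = 0.50: 2.028 × √(1/38) = 0.329 SD
- r = 0.75: 2.028 × √(0.5/38) = 0.233 SD

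The form at both visits is more precise across the whole assumed range, even at r = 0, because each subject contributes to both treatments.

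**Step 5: number of ratings that can be assigned to a treatment**

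One pooled form after Visit 2 gives 0 of 38. One form per session gives 38 × 2 = 76, the same number that the de-blinding questionnaire already yields.

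**The case against.** A reader might infer that neither schedule can give a CLRT-versus-sham comparison. The documents do not support that. A Visit 1 form completed after treatment can be linked to the period-1 assignment, because source documents carry a study ID (section 10.2) and the allocation is date-stamped (section 3). The result is a valid randomised comparison, only less precise. The missing visit field therefore matters only for the end-of-study timing.

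A reader might also take 0 of 38 as a fact about the trial. It holds only if a single pooled form is used. Section 3 gives the timing but not the number of copies, and one copy per treatment at completion could work. Each copy would have to name the visit, since blinded subjects cannot name the treatment. Nothing in the plan or on the form provides for this.

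Finally, a reader might infer that the blind goes unchecked or that the KEA result is in doubt. Neither follows. Section 6.2.3 has subjects report after each session whether they believe they received active treatment, and how certain they are. The treating investigator does not disclose the assignment, and subjects lie face down with eyes closed. Credibility is not an aim, an outcome or a variable in section 9.6.

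What remains after all this is the timing conflict, and the fact that one form given after both treatments does not serve the purpose stated for it. The de-blinding questionnaire does not fill that gap: it asks which treatment the subject thinks was given, not how logical or convincing that treatment seemed.

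**Conclusion.** The concern holds in a limited form, and it is minor. The timing conflict is plain on the face of the text. Following sections 3 and 6.2.5 with a single form defeats the form's stated purpose. Following section 6.1 leaves at most a period-1 comparison, with a half-width of about 0.61 to 0.66 SD, and only if the form comes after treatment. A form at each visit would narrow this to between 0.47 and 0.23 SD.

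The narrower figures rest on 38 completers, equal SDs and correlations that are assumed, not documented. The loss is confined to a supporting check on the sham; the primary KEA estimate is unaffected.

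**What to change.** Give the form at the end of both visits, after the post-treatment PPT and alongside the de-blinding questionnaire, so that no post-test is delayed. Record ID and visit on it, and point the instruction to the treatment received that day. Mark both visits in 6.1, add the form to both lists in 6.2.4, and bring section 3 and 6.2.5 into line.

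Add one sentence to section 9.6, for example: *Credibility scores will be summarised by treatment, with the within-subject CLRT-minus-sham difference and its 95% confidence interval.*

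Two further steps are optional. One is to estimate the difference from a mixed model with treatment and period as fixed effects and a random subject effect. The other is to have the paper form self-completed and sealed so the masked assessor does not read it. Sealing adds little, because the assessor already administers the de-blinding questionnaire.

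**Cost.** One extra four-item form per subject (at most 44 in all), one table row and a few sentences, with no added visit. There are two downsides. The wording of an adapted scale changes slightly. Ratings taken after the post-tests may also partly reflect change the subject has noticed, so a credibility difference could in part be a treatment effect. Item 2, which looks forward to success, is the most exposed to this.

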Assessments. KEA: The 90-90 Knee Extension Angle test is a functional assessment designed to assess lower extremity flexibility and is considered the gold standard for hamstring length (32). The participant will be in the supine position on a treatment table. The tested extremity (the right leg in each subject) will be placed in a 90° hip and 90° knee position with the contralateral lower extremity placed flat on the table. A digital inclinometer will be consistently placed at the level of the medial malleoli and the superior pole of the patella. The examiner will maintain 90° of hip flexion. Pelvic position will be monitored by palpation of the anterior superior iliac spine and lumbar spinous processes to maintain a neutral pelvic position. The examiner will passively extend the knee to the point of a "strong, but tolerable stretch," as reported by the subject. The examiner will read the angle of the inclinometer and record the mean value of three attempts. A greater angle indicates greater degree of flexibility.

Hand held Dynamometry (HHD) is currently considered a reliable and valid measurement of peak muscle contraction(33). The subject will be prone on the table with right leg bent to 90°. The tester will place the dynamometer (microFET2; Hoggan Health Industries, Salt Lake City, UT) at the heel of the participant and apply force to the heel, gradually increasing in 3 to 5 seconds. Participants will be instructed to resist the applied force and maximally contract the hamstring muscle against the HHD device. The test ends once they are no longer able to resist the force and the leg begins to move (break point). The investigator will record the mean value of three attempts.

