Device: The treatment device to be used in this study is a Class IIIB 810nm 200mW near-infrared GAAIAS diode laser (THOR Photomedicine Ltd, Great Britain) that is currently marketed in the US. The laser probe is FDA-cleared and classified as a non-significant risk device. The spot size is 0.0364 cm², and the treatment time is 30 seconds. Current best-practice recommendations for laser acupuncture(35) recommend a dosage between 1-4 J/cm² per point. Since the cranial reflex point (CRP) is a line of 2 cm, for the purposes of calculating dosage, we will treat it as a series of 10 connected points each with a diameter of 2mm. With the scanning rate of 2cm/s, each “point” on the line will receive 1/10 of each pass, totaling 3s (out of 30s total) exposure time per point. The dose per point for this intervention is calculated to be approximately **1.65 J/cm²**.

$$\text{Power Density} \left(\frac{J}{cm^2} \right) = \frac{\text{end power}(W) * \text{Time}(s) * \text{energy loss factor} \left(\frac{1}{cm} \right)}{\text{area}(cm^2)}$$

$$= \frac{0.2 W * 3s * 1}{0.0364 cm^2} = 1.65 \frac{J}{cm^2}$$

Random Allocation. At the first intervention visit, the research assistant will enter the subject’s assigned ID into an online computer program that will determine assignment to one of the two treatment periods. Using a random number sequence to generate a permuted block of 2-4, the program ensures

[figure not shown]

Fig.1 Location of bilateral cranial reflexes for hamstrings

equal numbers of subjects in each arm. The program documents treatment assignment in an un-editable form including a date stamp.

Masking. The research coordinator and treating investigator will be unmasked. All research assistants performing the assessments will be masked. Masking will be maintained in the random allocation procedure. The treating investigator will not indicate to subjects or assessor to which period the participant is assigned.

Remuneration. Subjects will receive an Amazon gift card worth \$25 upon completion of the second visit. If the subject completes only the first visit, they will be compensated a prorated amount with a card worth \$15.

The following patient-reported variables will be assessed:

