Appendix B.c: De-blinding Questionnaire (Ver. 0.1)

ID # _____

Date: _____

**CLRT Hamstring Study
De-blinding Questionnaire**

1. Do you believe you received the active treatment (CLRT) today?

☐ Yes ☐ No

2. How certain are you that you received the active treatment today?

Not at all certain				Somewhat certain				Absolutely certain		
0	1	2	3	4	5	6	7	8	9	10
										

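### The masked assessor administers the visit-1 de-blinding form, so a participant's guess could reach the person doing the visit-2 tests; the certainty item is also ambiguous after a 'No'

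*Combined protocol and SAP*

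**What the plan says.** The plan promises masked assessment twice. The Masking paragraph of section 3 states: "All research assistants performing the assessments will be masked". Section 6.2.3 states: "Subjects and assessors will be blinded to treatment allocation".

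Section 6.2.3 then gives the blinding check to the same assessors: "the participants will complete a de-blinding questionnaire administered by the assessor". The visit lists in section 6.2.4 put this form last at both visits, after the post-treatment knee extension angle (KEA), dynamometry (HHD) and pressure pain threshold (PPT).

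Section 5.2.2 lists as required: "Participation in both study arms of the crossover trial". On the primary outcome, section 3 says: "The examiner will read the angle of the inclinometer and record the mean value of three attempts".

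The form in Appendix B.c has two items. The first, answered yes or no, is "Do you believe you received the active treatment (CLRT) today". The second, scored 0 to 10, is "How certain are you that you received the active treatment today". Everyone answers the second item, whatever they answered to the first.

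**The concern.** In a two-period crossover, what a participant received at visit 1 determines what they receive at visit 2. A visit-1 'Yes' therefore points to sham at visit 2, and a 'No' points to active. If the assessor hears or reads that answer, they may start the visit-2 tests with an expectation about the condition.

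The outcomes leave room for an expectation to act. For KEA the examiner holds the hip, extends the knee to a tolerance the participant reports, and reads the inclinometer. HHD and PPT also depend on force the examiner applies. At stake is the masking of the visit-2 measurements, which are half of the planned outcome data and include the primary outcome.

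The second problem lies in the form. A participant who answers 'No' and is sure of it could mark 0 (not at all certain it was active) or 10 (entirely certain of the answer). Those scores would then say little about how well blinding held.

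**Working it through.** **Route of exposure.** Four statements, taken together, leave the route open:

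- Assessors are to be masked (section 3, Masking; section 6.2.3).
- The assessor administers the form after each session (section 6.2.3), last at each visit (section 6.2.4). The visit-1 answer therefore precedes every visit-2 test, while each visit's own tests precede that visit's form.
- Every participant receives both conditions (section 5.2.2).
- The nearest safeguard, in section 10.3.3, keeps the data-entry assistant away from participants. It does not cover who administers the form.

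No section provides for a different assessor at visit 2, a sealed form, or administration by staff who do no testing. The schedule in section 6.1 lists a research assistant at both visits without saying whether it is the same person.

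**Size, as an illustration.** The documents give neither the accuracy of the guesses nor the examiner's response to them, so both are assumptions:

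- *p*: proportion of visit-1 guesses that are correct.
- *b*: net difference, in degrees, in the visit-2 pre-to-post KEA change between participants the assessor believes are on active and those believed to be on sham. Half is added for the first group and half subtracted for the second.

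Among participants truly on active at visit 2, the mean shift is (b/2)p − (b/2)(1 − p) = b(2p − 1)/2. Among those truly on sham it is the negative of this. The visit-2 contrast is therefore off by b(2p − 1) and the visit-1 contrast by 0. The crossover estimate averages the two:

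bias = b(2p − 1)/2

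A simulation reproduced this formula for p from 0.5 to 0.9 and b of 1°, 2° and 5°.

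**Standard error, from section 9.2** (SD 15°, correlation 0.75, n = 38):

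- SD of the paired difference = 15 × √(2 × (1 − 0.75)) = 10.61°.
- SE = 10.61/√38 = 1.72°.
- Check on these inputs: the paired t-test has power 0.808 for 5° at n = 38, which agrees with the plan's figure of at least 80%.

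**False-positive rate with no true effect:** P(Z > 1.96 − bias/1.72) + P(Z < −1.96 − bias/1.72). For bias 1.0°, bias/SE = 0.58, giving 0.084 + 0.0055, or about 0.09.

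For b = 2°:

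| p | Bias | False-positive rate |
|---|---|---|
| 0.5 | 0° | 5.0% |
| 0.6 | 0.2° | 5.2% |
| 0.7 | 0.4° | 5.6% |
| 0.8 | 0.6° | 6.4% |
| 0.9 | 0.8° | 7.5% |
| 1.0 | 1.0° | about 9% |

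With b = 1° and p = 0.9, the bias is 0.4°. With b = 5° and p = 0.9, it is 2.0° and the rate is about 21%. The effect the trial is powered for is 5°.

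The table assumes that every participant meets the same assessor twice and that the assessor acts on every guess. If that holds for only a fraction of participants, the bias shrinks by that fraction.

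**Certainty item.** Section 6.2.3 and Appendix B.c both word it as certainty of having received active treatment, with no branch after 'No'. Two readings are open to someone sure of having had sham, and they sit at opposite ends of the scale. The zero anchor adds to this: section 6.2.3 labels it *absolutely uncertain*, which suggests no idea either way, while the form prints *Not at all certain*, which can be read as doubting that the treatment was active. Section 9.6 gives no scoring rule that would settle the matter.

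**The case against.** The strongest reply is that a guess is not an allocation. Nothing on the form reveals the assignment, and if blinding works the guesses are at chance and the bias is exactly zero. The form comes after the post-tests, so visit 1 is protected and no answer can affect tests at the same visit. The précis speaks of independent examiners and section 3 of research assistants, both plural, so a different person may test at visit 2. Even the same person would have to remember an answer from a week or more earlier. The form is a tick-box sheet that participants complete, and administering it need not mean reading it. All of this stands, and it limits the point to a possible exposure of unknown size.

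It does not remove the point, because nothing in the plan closes the route and administration by the assessor is what opens it.

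A reader might go further and infer that assessors are unmasked for all visit-2 data, or that the false-positive rate is about 9%. The documents support neither. The first needs the same assessor at both visits and sight of the answers. The second needs, in addition, every guess to be correct and acted on, with a 2° shift that no document supplies.

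A reader might also infer that the certainty scores are useless as a whole. That is too strong. Scores after 'Yes' can be interpreted, and the yes/no item can be tabulated by treatment received. Section 9.6 plans no analysis of either item, so no planned efficacy estimate depends on them.

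**Conclusion.** The point holds as an avoidable procedural risk to assessor masking at visit 2, plus one ambiguous question. The text establishes who administers the form, when, and that no safeguard covers it. It does not establish that any assessor will see a guess and then test the same participant, so the supportable wording is that visit-2 tests could be exposed.

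The consequence cannot be sized from the documents. Under an assumed 2° shift the bias is nil at chance guessing and stays below 1.0° unless every guess is correct. Larger assumed shifts give larger figures. The case for changing the plan does not depend on choosing among these values: the instrument meant to check blinding should not be able to weaken it, and preventing this costs almost nothing. The defect in the certainty item is confined to scores that follow a 'No' and to the mismatched zero anchor.

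**What to change.** - **Section 6.2.3:** replace administration by the assessor with self-completion by the participant, either in REDCap (section 10.2 already has participants completing online questionnaires during visits) or on a form the participant seals. State that assessors may not see any response until database lock.
- **Appendix B.c, item 2:** reword to *How certain are you of your answer to question 1?* and change the description in section 6.2.3 to match.
- **Anchors:** use the same wording for the zero point in section 6.2.3 and on the form.

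The cost is a short change to one section and a revision of a one-page form. It needs no extra staff or visits and leaves treatment and sample size unchanged.
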